1.5 Study Design

This is a multi-center, open-label, Phase I/II study. Phase 1 consists of a 3+3 dose de-escalation design to determine the dose of copanlisib for use in combination with nivolumab. Approximately 6-18 subjects with solid tumors will be treated in Phase I and will be monitored for dose limiting toxicities (DLTs) through their first cycle of treatment. Complete information on the definition of DLTs and dose de-escalation rules can be found in **Section 4.3**.

The Phase II portion of the study will evaluate the safety and clinical activity of copanlisib and nivolumab in two cohorts of patients with previously treated metastatic colon cancer. Cohort A will enroll patients with PI3K mutation and Cohort B will enroll patients with wildtype PI3K status. Twenty-one patients are targeted for enrollment in each cohort, for an approximate total of 42 patients in Phase II. Enrollment in Phase II will be initiated once the recommended phase II dose (RP2D) has been determined in Phase I.

For all patients, the study will consist of a screening period, a treatment period, and a follow-up period. Screening evaluations will be done within 28 days prior to the start of study treatment.

Each treatment cycle is 28 days. Patients in both Phase I and Phase II will receive nivolumab on Day 1 of each cycle (every 4 weeks) and copanlisib on either Day 1, Day 8, and Day 15 of each cycle (3 week on, one week off) or on Day 1 and 15 of each cycle (every 2 weeks), depending on the dose level and RP2D. Complete information on study drug administration, schedule, and dosing can be found in **Section 4.2**.

Phase II enrollment will be carried out in 2 stages so that the study can terminate early if the combination of copanlisib and nivolumab is not sufficiently effective. In the first stage, 12 subjects will be accrued to each cohort. If there are no responders among the first 12 patients, the study will be terminated for futility. Otherwise, 9 additional patients will be accrued for a total of 21 treated subjects. If ≥ 3 out of the 21 patients have a response, then the trial will be considered a success for that cohort.

Clinical and immune responses will be evaluated at baseline and during treatment through tumor assessments, biopsies, and PBMC and plasma collection. Tumor assessments will be made using RECIST 1.1.

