4.2 Agent Administration

There will be two phases in this study: A Phase I dose-finding stage followed by a Phase II expansion.

Copanlisib will be administered as a 60 minute IV infusion (-5min/+10min) at the doses and days shown in **Table 1** and **Table 2** below. Subjects should be observed for a minimum of 30 minutes after administration of Copanlisib prior to administration of nivolumab.

Nivolumab 480 mg will be administered as a 30 minute IV infusion (-5min/+10min) on Day 1 of each 28 day cycle.

The Pharmacy Manual contains specific instructions for the preparation and administration of these study drugs.

[figure not shown]
Study treatment should be administered after all procedures/assessments have been completed for that visit as detailed on the Study Calendar (**Section 8**). Study treatment may be administered up to 3 days before or after the scheduled Day 1 of each cycle, up to 1 day after the scheduled Day 8, or up to 3 days after Day 15 of each cycle due to administrative reasons as long as there is a minimum of 7 days between copanlisib infusions.

All trial treatments will be administered on an outpatient basis.

Phase I – Dose De-Escalation

Phase I will use a standard 3+3 design. The initial dose being tested is the recommended phase 2 dose of both study drugs as single agents, so the doses of copanlisib and nivolumab will not escalate higher than dose level 1. However, if the recommended phase II dose (RP2D) is exceeded in dose level 1, the dose of copanlisib will de-escalate as indicated below in Table 1. A maximum of 18 eligible subjects will be enrolled into this phase. All patients enrolled at each dose level will be evaluated for dose limiting toxicities (DLTs) during the first 28 day cycle for the purpose of determining the RP2D when given concurrently with nivolumab. DLTs and dose de-escalation rules are defined in **Section 4.3** and **Table 3**, respectively.

[figure not shown]
Table 1 – Phase I Dose Levels and Regimen (listed in order of administration)

Phase II – Expansion Cohorts

Phase II will enroll patients with mismatch-repair proficient colorectal cancer with known PI3K-mutation status. 21 patients will be enrolled into Cohort A (PIK3CA mutation) and 21 patients will be enrolled into Cohort B (PIK3CA WT). Both cohorts will receive the same treatment regimen. The dose of copanlisib given in Phase II will be the RP2D determined during Phase I of this study.

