4.4 Dose Modification and Toxicity Management

4.4.1 Dosing Delays and Modifications

Study treatments are scheduled on a 3 weeks on, 1 week off schedule.

- Start of a treatment cycle (Day 1) will be delayed for toxicity until retreatment criteria are met. The Principal Investigator must approve retreatment if delays last longer than 1 week. If delays are required due to toxicity related to one study drug but not the other, all study treatment will be delayed.
- If the day 8 or day 15 dose of copanlisib needs to be delayed longer than 2 days due to toxicity, the dose(s) should be skipped and the remainder of the cycle continued once retreatment criteria are met. The intention here is to keep the length of each cycle to 4 weeks, when possible. Skipped doses will be documented in the study database.

There will be no dose reductions to nivolumab. Dose reductions to copanlisib will use the dose levels outlined in **Table 1** and dose reduction criteria outlined in **Table 4**. If a patient is already receiving the lowest dose level of copanlisib and meets criteria for further decrease, study treatment will be discontinued permanently. There will be no dose re-escalation for DLTs. Dose re-escalation may be allowed for non-DLTs at the PI's discretion after patient has fully recovered from the toxicity and in the absence of any other

adverse events that require dose-reduction, with the exception of non-infectious pneumonitis.

Dosing of study therapy will be delayed for the following criteria (or **Table 4** criteria):

- AST/ALT $>3 \times$ ULN
- Total bilirubin $> 1.5 \times$ ULN ($> 2.0 \times$ ULN for subjects with Gilbert's syndrome)
- Creatinine $> 1.5 \times$ ULN or GFR < 40 mL/min/1.73 m²
- Hemoglobin < 8 g/dL
- ANC < 1250 /uL (day 1) and < 1000 (days 8 and 15) – hold both study drugs
- Platelets $< 75 \times 10^3$ /uL
- Fasting Glucose (Cycle 1 Day 1) >125 mg/dL (non-diabetic patients) or ≥ 160 mg/dL (diabetic patients)
- Fasting glucose (all other days) > 160 mg/dL
- CMV PCR > 500 IU/mL (tested each cycle for cycles 1-6, and every 3 months thereafter)
- Any Grade ≥ 2 non-skin, nivolumab-related adverse event, with the following exceptions:
 - Grade 2 fatigue
 - Grade 2 lab abnormalities
 - Grade 2 hypothyroidism or thyroiditis
- Any Grade ≥ 3 skin nivolumab-related AE
- Any Grade ≥ 3 nivolumab-related laboratory abnormality with the following exceptions:
 - Grade 3 lymphopenia

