Drug-related AEs	Grade (CTCAE v5.0) or measurement	Action taken to study drugs	Retreatment Dose Level	AE management	Monitor and follow-up
	Grade ≥ 3	Withhold	Decrease by one dose level at the PI's discretion	
 • Treatment with transfusion or growth factors allowed at PI's discretion 	
Other non-hematological toxicities	Grade 3	Withhold	1 st : no dose change 2 nd -3 rd : decrease by one dose level 4 th : discontinue		
	Grade 4 or any toxicity requiring delay for >21 days	Permanently discontinue	N/A		

 1. Persistent occurrence is defined as repeated post-infusion blood glucose measurements taken at different times during the cycle despite optimal glucose-lowering therapy in consultation with endocrinologist 2. Infusion may proceed/resume on scheduled day if BP recovers to <150/90 mmHg for 2 consecutive measurements and symptoms (if present) resolve. 3. Despite maximum supportive therapy 4. Thrombocytopenia, neutropenia, febrile neutropenia, anemia, INR or PTT with bleeding 
General instructions:
 
 • For situations where drug is withheld due to a copanlisib-related AE, treatment can be resumed after AE has been reduced to Grade 1 or 0 unless otherwise indicated. Treatment should be permanently discontinued if AE does not resolve within 12 weeks of last dose. • If patient is already on lowest dose level and meets criteria for further decrease, study drug will be discontinued permanently. • Dose re-escalation may be allowed at the PI's discretion after patient has fully recovered from the toxicity and in the absence of any other adverse events that require dose-reduction, with the exception of non-infectious pneumonitis. • Abbreviations: SGLT2 = Sodium/Glucose co-transporter 2; DPP4 = Dipeptidyl peptidase 4; PJP= pneumocystis jiroveci pneumonia 					

In order to standardize the management of AEs for all subjects, treatment management algorithms are included in **Appendix C**. Additional AE treatment management algorithms included in the nivolumab IB might be considered for individual cases.

Subjects who require a delay in study treatment should be re-evaluated weekly or more frequently if clinically indicated and resume dosing when re-treatment criteria are met.

Subjects may resume treatment with study drug when the nivolumab-related AE(s) resolve to grade ≤ 1 or baseline value, with the following exceptions:

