4.4.4 Additional Toxicity Monitoring and Prevention

4.4.4.1 Glucose and Diet Monitoring

Period	Fasting \geq 12 h required before first glucose measurement	Pre-dose glucose levels
Day 1 of Cycle 1	Yes	<125 mg/dL (non-diabetic patients) <160 mg/dL (diabetic patients)
Subsequent infusions after Cycle 1 Day 1	Yes	<160 mg/dL (fasting) <200 mg/dL (non-fasting)

Fasting refers to a \geq 12 hour fast. Non-fasting status includes any caloric intake such as meals, juice, snack, as well as other caloric intake not consistently called a meal.

From Cycle 1 Day 1 onwards, glucose measurements may be done either by laboratory analysis or in capillary blood.

Because of its inhibitory effect on the PI3K α -isoform, which is implicated in insulin metabolism, copanlisib infusions could be associated with a temporary increase in blood glucose. Addition of a meal in close proximity to copanlisib infusion may exacerbate glucose increase.

On infusion days a low calorie or low carbohydrate diet is recommended. It is recommended that timing and content of caloric intake as well as additional glucose testing (if clinically indicated) on infusion days is monitored by the investigators based on glucose response patterns during prior treatment days. Consultation with a diabetologist or endocrinologist is advised.

All glucose measurements, oral glucose lowering medication and/or insulin administration, if applicable, fasting/non-fasting status, and meal intake timing on infusion days will be collected as part of the clinical source documentation.

Glucose monitoring on study

Management of hyperglycemia and dose delay parameters are outlined in **Table 4**

The following assessments should be performed on Day 1, 8, and 15 of each cycle before receiving copanlisib unless otherwise specified:

- Patients should be fasting for at least 12 hours prior to the pre-dose glucose measurement. For details on fasting requirements and glucose measurement during C1D1 please refer to **Table 6**
- Blood glucose will be measured at 0 hours (pre-dose) and 1 hour after completion of copanlisib (+/- 15min) infusion. If 1 hour post-infusion blood glucose is \geq 35 mg/dL higher than pre-dose level, recheck in another hour (2 hours post-infusion) to ensure decline in blood glucose. Additional measurements to be performed as clinically indicated.

NOTE: If patient needs to take a low glycemic meal, then glucose test should be taken prior to meal intake.

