6.1.5 Preparation

Nivolumab injection should be diluted with 0.9% Sodium Chloride Injection, USP or 5% Dextrose Injection, USP to protein concentrations as low as 1 mg/mL. Care must be taken to assure sterility of the prepared solution as the product does not contain any antimicrobial preservative or bacteriostatic agent. No incompatibilities between nivolumab and polyolefin bags have been observed. Recommended safety measures for preparation and handling of nivolumab include laboratory coats and gloves. Detailed instructions on the preparation of nivolumab for administration will be provided in the Investigator's Brochure.

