6.2.2 Mode of Action

Copanlisib is a pan-class I phosphatidylinositol 3-kinase (PI3K) inhibitor with predominant and potent activity against the PI3K- δ and PI3K- α isoforms. The PI3K pathway is a

prominent pathway that promotes cellular survival and is found to be constitutively activated in many cancer types. Inhibition of this pathway is expected to lead to impaired cellular uptake of glucose, with a subsequent reactive rise in plasma insulin and glucose levels.

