6.2.8 Route of Administration

Copanlisib is administered in a normal saline solution, intravenously, over 1 h. No intravenous glucose preparations should be administered on the days of infusion.

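### Section 6.1.5 allows 5% dextrose as nivolumab diluent, but every scheduled nivolumab dose falls on a copanlisib day, when Section 6.2.8 bars intravenous glucose

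*Combined protocol and SAP*

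**What the plan says.** - **Diluent.** Section 6.1.5 permits nivolumab to be diluted with "0.9% Sodium Chloride Injection, USP or 5% Dextrose Injection, USP to protein concentrations as low as 1 mg/mL". It attaches no condition to either choice and leaves detailed preparation steps to the Investigator's Brochure. Section 4.2 also refers to a Pharmacy Manual.
- **Glucose restriction.** Section 6.2.8 describes the copanlisib infusion and adds: "No intravenous glucose preparations should be administered on the days of infusion". From its position, this means copanlisib infusion days.
- **Schedule.** Section 1.5 says patients "will receive nivolumab on Day 1 of each cycle (every 4 weeks) and copanlisib on either Day 1, Day 8, and Day 15", or copanlisib on Days 1 and 15 only, depending on dose level. Both study calendars in Section 8 also place the two drugs together on Day 1.
- **Sequence.** Section 4.2 gives copanlisib first: "Subjects should be observed for a minimum of 30 minutes after administration of Copanlisib prior to administration of nivolumab".
- **Delays.** Section 4.4.1: "If delays are required due to toxicity related to one study drug but not the other, all study treatment will be delayed".
- **Glucose monitoring.** Section 4.4.4.1 measures glucose before the dose and 1 hour (+/- 15 min) after copanlisib ends. If the value has risen by 35 mg/dL or more, staff are to "recheck in another hour (2 hours post-infusion) to ensure decline in blood glucose".

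**The concern.** A permission in one drug's section conflicts with a safety instruction in the other's. A pharmacist who follows 6.1.5 in good faith and chooses dextrose would give intravenous glucose on a day when 6.2.8 says not to.

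The restriction has a stated pharmacological basis. On copanlisib, Section 6.2.2 says: "Inhibition of this pathway is expected to lead to impaired cellular uptake of glucose". Section 4.4.4.1 accordingly asks for a 12-hour fast, recommends a low-calorie or low-carbohydrate diet on infusion days, and schedules post-infusion checks. A dextrose bag works against those controls. It could raise the 1-hour value and trigger the recheck, or blur the 2-hour value that is meant to confirm a decline. In either case, part of a rise attributed to copanlisib would come from the diluent.

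**Working it through.** The plan gives no figure for this point, so there is none to reproduce. The check has four steps.

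**1. Do the days overlap?** Nivolumab days are {1}. Copanlisib days are {1, 8, 15} or {1, 15} (Section 1.5). Day 1 is in both sets, so all scheduled nivolumab doses fall on a copanlisib day. A toxicity delay caused by either drug moves both (Section 4.4.1).

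**2. How much dextrose?** Inputs: dose 480 mg (Section 4.2), vial strength 10 mg/mL (Section 6.1.3), and a floor of 1 mg/mL after dilution (Section 6.1.5). The protocol fixes no final concentration, so the values above 1 mg/mL are assumptions.

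- Drug volume = 480 / 10 = 48 mL
- Bag volume = 480 / concentration
- Dextrose (g) = (bag volume - 48) x 0.05

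| Final concentration | Bag | Diluent | Dextrose |
|---|---|---|---|
| 1 mg/mL (floor) | 480 mL | 432 mL | 21.6 g |
| 2 mg/mL | 240 mL | 192 mL | 9.6 g |
| 3 mg/mL | 160 mL | 112 mL | 5.6 g |
| 5 mg/mL | 96 mL | 48 mL | 2.4 g |
| 10 mg/mL (undiluted) | 48 mL | 0 mL | 0 g |

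**3. How much is in by the glucose checks?** Let copanlisib end at time 0, nivolumab start at s minutes and run for d minutes. The share infused by time t is (t - s) / d, limited to the range 0 to 1. With the nominal d = 30:

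| Start s | t = 45 | t = 60 | t = 75 | t = 120 |
|---|---|---|---|---|
| 30 min | 50% | 100% | 100% | 100% |
| 45 min | 0% | 50% | 100% | 100% |
| 60 min | 0% | 0% | 50% | 100% |
| 90 min | 0% | 0% | 0% | 100% |
| 105 min | 0% | 0% | 0% | 50% |

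The columns 45, 60 and 75 span the +/- 15 min window of the 1-hour check; 120 is the recheck. With the slowest permitted infusion (30 + 10 = 40 min) and s = 30, the shares at 45, 60 and 75 min are 38%, 75% and 100%.

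**4. Could this reach the 35 mg/dL trigger?** The documents give no distribution volume. Assume V = 10 to 18 L and no clearance, which makes the result an upper bound for the full load:

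- Rise (mg/dL) = g x 1000 / (V x 10)
- 21.6 g: 21,600 / 180 = 120 to 21,600 / 100 = 216
- 9.6 g: 53 to 96
- 5.6 g: 31 to 56
- 2.4 g: 13 to 24
- Dextrose needed for 35 mg/dL = 35 x V x 10 / 1000 = 3.5 to 6.3 g

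On that assumption a 5 mg/mL bag could not reach the trigger alone, 3 mg/mL is borderline, and 1 or 2 mg/mL could.

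**The case against.** The strongest reply is that the two sections can be followed together. One offers a choice of diluents, the other is a specific restriction, and saline meets both. No site is forced into a breach, so what is missing is arguably only a cross-reference. That is correct as far as it goes. But 6.1.5 as written still grants a permission that cannot properly be used at any scheduled dose, and the restriction sits in the other drug's section.

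Second, the working preparation instructions are in the Pharmacy Manual and the Investigator's Brochure, which were not supplied and may already require saline. This stands. Confidence applies to the conflict in the protocol text, not to any claim that dextrose has been used.

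Third, the glucose rises rest on assumed concentrations, an assumed volume and no clearance, and the rise figures use the full load, although half or none may be in at the 1-hour check if nivolumab starts later. This also stands. The figures are upper bounds, and the conflict does not depend on them.

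Fourth, the consequences are small. Table 4 in Section 4.4.1 makes no dose change for symptomatic or persisting glucose above 250 mg/dL. It reduces the dose only for persistent values above 500 mg/dL repeated after two infusions, and its footnote states: "Persistent occurrence is defined as repeated post-infusion blood glucose measurements taken at different times during the cycle". Section 4.3 exempts transient hyperglycemia from dose-limiting toxicity. A Day 1 load alone is therefore unlikely to drive either decision. This limits the weight of the point but does not remove it.

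Finally, 6.2.8 uses advisory wording, and the joint-delay rule covers toxicity only, not administrative shifts within the Day 1 window. The conclusion is accordingly confined to doses given as scheduled.

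**Conclusion.** The concern holds and should be fixed. Under both schedules every planned nivolumab dose shares a day with copanlisib, so the dextrose option in 6.1.5 is never consistent with 6.2.8 as scheduled, and nothing in the supplied text says so.

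If dextrose were used, the avoidable load would lie between 2.4 g and 21.6 g for concentrations from 5 down to 1 mg/mL, the last being an extreme case. Depending on start time, it could affect the 1-hour check or the 2-hour recheck. Whether it could reach the recheck threshold by itself depends on the bag concentration and on the assumed 10 to 18 L volume without clearance.

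This is a matter of safety conduct and of interpreting post-dose glucose. It does not affect the primary endpoint, the sample size or the error rates.

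**What to change.** In Section 6.1.5, delete the 5% dextrose option and state that in this trial nivolumab is diluted only with 0.9% sodium chloride, with a reference to Section 6.2.8. Align the Pharmacy Manual if it differs. With saline only, the dextrose given with nivolumab is 0 g and both sections are met.

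If dispensing records show that any past dose was prepared with dextrose, note this when interpreting that day's post-dose glucose values.

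The cost is one sentence in the protocol and a pharmacy memo. Saline is already a listed diluent, so no new supply is needed. The only extra work is the check of dispensing records.

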6.1.6 Storage and Handling Requirements

Clinical supplies must be stored in a secure, limited-access location. Nivolumab vials must be stored at a temperature of 2°C to 8°C and should be protected from light and freezing. If stored in a glass front refrigerator, vials should be stored in the carton. Receipt and dispensing of trial medication must be recorded by an authorized person at the trial site. Clinical supplies may not be used for any purpose other than that stated in the protocol.

6.1.7 Stability

The administration of nivolumab infusion must be completed within 24 hours of preparation. If not used immediately, the infusion solution may be stored under refrigeration conditions (2°-8°C, 36°-46°F) for up to 24 hours, and a maximum of 8 hours of the total 24 hours can be at room temperature (20°-25°C, 68°-77°F) and room light. The maximum 8-hour period under room temperature and room light conditions includes the product administration period.

6.1.8 Route of Administration

Nivolumab is to be administered as a 30 minute IV infusion, using a volumetric pump with a 0.2/0.22 micron in-line filter at the protocol-specified dose. It is not to be administered as an IV push or bolus injection. At the end of the infusion, flush the line with a sufficient quantity of normal saline.

6.1.9 Returns and Reconciliation

The investigator is responsible for keeping accurate records of the clinical supplies received from BMS or designee, the amount dispensed to and returned by the participants and the amount remaining at the conclusion of the trial.

Upon completion or termination of the study, all unused and/or partially used investigational product will be destroyed at the site per institutional policy. It is the Investigator's responsibility to arrange for disposal of all empty containers, provided that procedures for proper disposal have been established according to applicable federal, state, local and institutional guidelines and procedures, and provided that appropriate records of disposal are kept. BMS will be notified of all destruction of study drug.

6.2 Copanlisib

6.2.1 Agent Accountability

The investigator shall take responsibility for and shall take all steps to maintain appropriate records and ensure appropriate supply, storage, handling, distribution and usage of investigational product in accordance with the protocol and any applicable laws and regulations.

